Sex differences in BAT: In rodents, BAT activity is typically higher in females than males.^{69,81} In humans, retrospective studies have reported that the prevalence of BAT is greater in women than men but this sex difference diminishes with age, suggesting a potential role of female sex hormones.^{1,18,19,59,63,64} Conversely, acute cold exposure studies in humans have suggested that the volume of metabolically active BAT and BAT glucose uptake are similar in men and women.¹⁶ However, this may be attributed to limitations in the cold exposure protocols used. For example, one particular study recently reported that glucose uptake in BAT during a mild cold exposure was 50% lower in women compared to men. However, cold-induced thermogenesis (CIT, the increase in energy expenditure upon cold exposure) was also lower in women compared to men (0.3 vs. 0.9 kJ/min), suggesting the cold stimulus was not adequate to stimulate BAT in the women.³⁰

Evidence for regulation of BAT by estrogens: Several lines of evidence suggest that sex hormones regulate BAT activity.^{67,68,84,87} Androgens and estrogens exert opposing effects in brown adipocytes.^{51,70} Testosterone reduces UCP1 expression and thermogenic activity, whereas E₂ has the opposite effects.^{67,68,70} BAT function is compromised when ER α signaling is disrupted.^{13,90} Additionally, OVX rats have decreased BAT thermogenic activity and UCP1 expression in brown adipocytes,^{32,56,62,94} but these effects are reversed by E₂ treatment.^{3,27,42,46,87}

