CIT varies with E₂: We recently performed a pilot study in healthy, premenopausal women (n=5; 31 \pm 6 yr.; BMI 24.3 \pm 4.5 kg/m²) to determine the effects of ovarian hormone suppression on REE, CIT, and BAT activity. Before and after 3 mo of GnRH_{AG}, participants underwent a 2-hr cooling protocol using a surgical cooling vest filled with water (~16–18° C). Following GnRH_{AG}, REE decreased from 1382 \pm 218 kcal/d to 1341 \pm 209 kcal/d; the decrease (-41 \pm 160 kcal/d) was similar in magnitude to that observed in response to 5 mo of GnRH_{AG}+PL in the study described above (-57 \pm 105 kcal/d). CIT was also attenuated (350 \pm 228 vs. 302 \pm 139 kcal/d, Figure 4). We also performed ¹⁸FDG PET/CT measurements to demonstrate the feasibility of measuring BAT activity with this protocol. After GnRH_{AG}, no significant differences in ¹⁸FDG uptake were observed, but ¹⁸FDG uptake in BAT decreased in 3 of the 5 individuals studied (Figure 5). There are two limitations to consider in this pilot study. Firstly, the period of hormone suppression may have been too short to invoke substantial changes in BAT activity and CIT, because a single injection of GnRH_{AG} produces an initial sex hormone flare (for up to 3 wk) followed by continuous suppression with additional doses of GnRH_{AG}. **In the proposed study, we will use a longer period of ovarian suppression (6 mo) (SA3, exploratory).** Secondly, the use of ¹⁸FDG PET/CT to study BAT metabolism is influenced by the energy status of the BAT. Because FM increased following GnRH_{AG}, BAT TG content may have also increased, which will reduce ¹⁸FDG uptake independent of any changes in BAT metabolism.⁴ **In the proposed study, in addition to ¹⁸FDG, we will use PET to measure clearance of the tracer ¹¹C-acetate in BAT, which is not dependent on the energy status of the tissue and provides a direct measure of BAT thermogenesis.** We expect to see a more clear suppression of BAT thermogenesis with a more prolonged period of ovarian suppression (pre- vs. postmenopausal women, **SA1 and SA2; 6 mo**).

[figure not shown]

Fig 3. ¹¹C-acetate uptake during warm and cold-stimulated conditions. Ouellette et al., J Clin Invest, 2012

[figure not shown]

Fig 4. Cold-induced thermogenesis in pre-menopausal women before and after 3 mo. GnRHAG treatment.

[figure not shown]

Fig 5. Change in maximal standardized uptake values (SUV) of ¹⁸FDG in BAT in pre-menopausal women N=5) before and after 3 mo. GnRHAG treatment.

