CTRIC imaging center and then be instrumented with wireless temperature sensors (Thermochron iButton model DS1922H; Maxim integrated, San Jose, CA, USA) and sEMG electrodes (Delsys, EMG System, Natick, MA, USA). Temperature sensors will be placed on the forehead, chest, forearm, back of the hand, lower back and quadriceps to measure mean skin temperature.⁶⁰ sEMG electrodes will be placed on the belly of 8 large muscles known to contribute significantly to shivering during cold exposure (*m. trapezius*, *m. deltoideus*, *m. sternoclastomastoid*, *m. pectoralis major*, *m. rectus abdominis*, *m. vastus lateralis*, *m. vastus medialis*, *m. rectus femoris*).²⁹ Participants will then be fitted with the liquid-conditioned suit, swallow a telemetric thermometry capsule to measure core temperature (Vital Sense monitor and Jonah temperature capsule, Mini Mitter Co., Inc., Bend, OR, USA) and will perform a series of maximal voluntary contractions (MVCs) of each of the eight muscles being recorded by sEMG for normalization of the shivering measures. Indwelling catheters will then be placed in an antecubital vein for tracer infusions.

The liquid-conditioned suit will be perfused with 18° C water for 210 min (min 0-210). This is expected to induce a thermogenic response (~75% increase in REE) but minimize shivering. In our previous study using the same cold stimulus, mean skin temperature was 33.1±0.3° C at room temperature, and decreased to 28.6±0.3 °C during cold exposure; shivering, measured using sEMG was minimal (1.6% of MVC); and REE increased from 6.7±0.3 to 12.2±0.8 kJ·min⁻¹ (~2300 to 4170 kcal·d⁻¹).⁶ This suggests that the contribution of NST to CIT was substantial and at its highest level.⁹ Participants will be monitored continuously for shivering using sEMG collected using a digital recorder (Trigno Wireless EMG System, Delsys, Inc., Boston, MA). REE will then be measured at minute 90 to determine CIT (cold-simulated REE – baseline REE). At time 120 min, a fasted blood sample will be obtained for the measurement of thyroid hormones (TSH, total T₃, free T₄) and markers of lipolysis (free fatty acids and glycerol). Following the blood sample, a ~185 MBq bolus of ¹¹C-acetate will be injected intravenously, followed by a 30 min list-mode dynamic PET acquisition. This will be immediately followed by a regional CT scan

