Sample size justification and power analyses – Sample size calculations and power analyses were performed using SAS 9.4 (SAS Institute, Inc., Cary, NC). For our estimate of effect size, we refer to our previous study that measured CIT in the follicular and luteal phases (Figure 5).⁸ In that study, CIT was higher during the luteal phase ($2530 \pm 524 \text{ kcal} \cdot \text{d}^{-1}$ vs. $2225 \pm 440 \text{ kcal} \cdot \text{d}^{-1}$). Unfortunately, we did not measure BAT activity. Because there were no differences in shivering in this study, we will assume differences in CIT were due to differences in NST; we also assume that this reflects differences in BAT activity. Using a pooled SD of 484 kcal/d, 32 evaluable participants per group (64 total) will provide 80% power to detect a difference of 305 kcal/d in CIT between pre- and postmenopausal women using a 2-sided t-test and a type I error rate at 0.05. Assuming a dropout rate of 15%, 38 participants per group will need to be enrolled to yield the desired sample size of 64 participants. The primary endpoint is BAT oxidative metabolism (¹¹C clearance rate, expressed per mL of BAT per s⁻¹). In our previous study of 12 men, BAT oxidative metabolism increased during cold exposure from 0.35 ± 0.13 to 0.74 ± 0.19 (mean \pm SEM).⁶ Using a pooled SD of 0.45, we estimate that we will have 80.0% power to detect a difference between groups of 0.32 during thermoneutral conditions. Using a pooled SD of 0.66, we will have 84.7% power to detect a difference between groups of 0.50 during cold exposure. In another study, BAT oxidative metabolism at room temperature was 0.35 in lean men vs. 0.05 in overweight men with T2D.¹⁰ We have also reported that BAT oxidative metabolism increased in lean men from 0.73 to 1.59 following a 4-week cold acclimation.⁷ Thus, we consider this to be a meaningful effect size to examine differences in BAT oxidative metabolism between groups during thermoneutral conditions and during cold exposure. A secondary endpoint is BAT activity volume. In our previous study, BAT activity volume was $57 \pm 16 \text{ ml}$ (mean \pm SE).⁶ Using a pooled SD of 55 ml, the study will have 80.0% power to detect a difference of 39 mL between groups. In another study, we reported that BAT activity volume was 48 vs. 4 ml in young healthy men compared to older men with T2DM.⁵ Thus, we consider this to be a meaningful effect size.

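### The stated 80% power for 305 kcal/d in CIT is about 70% on the plan's own two-sided inputs, and the figures behind it are not on the scale of CIT as the protocol defines it

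*Combined protocol and SAP*

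**What the plan says.** The sample-size paragraph in Section IV.F opens with CIT. It takes its effect size from an earlier study of women in two menstrual-cycle phases: "In that study, CIT was higher during the luteal phase", at 2530 ± 524 against 2225 ± 440 kcal/d. It then gives the inputs, "Using a pooled SD of 484 kcal/d, 32 evaluable participants per group (64 total" in all), and states that this sample "will provide 80% power to detect a difference of 305 kcal/d in CIT between pre- and postmenopausal women". The test named is a two-sided t-test at the 0.05 level. With 15% dropout it arrives at 38 enrolled per group.

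The same paragraph goes on to the primary endpoint, BAT oxidative metabolism. It claims 80.0% power for a difference of 0.32 (SD 0.45) at thermoneutrality and 84.7% for 0.50 (SD 0.66) in the cold. For BAT activity volume it claims 80.0% for 39 mL (SD 55).

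CIT is defined twice elsewhere, both times as an increment. Section III (Sex differences in BAT) calls it "the increase in energy expenditure upon cold exposure". Section IV.D (Visit #2) says "REE will then be measured at minute 90 to determine CIT", followed in parentheses by cold REE minus baseline REE. Section IV.A lists CIT among the secondary outcomes.

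**The concern.** Two things in the CIT statement look wrong, and they are independent of each other.

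The first is arithmetic. A difference of 305 with an SD of 484 is a standardised effect of 0.63. The primary-endpoint statement in the same paragraph needs 0.32/0.45 = 0.711 to reach 80.0% at the same sample size. Both cannot be right for the same test.

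The second is the variable. Values above 2200 kcal/d are very large for a rise over rest in women whose resting expenditure the protocol puts near 1400 kcal/d. If they describe another quantity, their SD cannot simply be carried over to CIT.

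At stake is how a CIT result is read. The paragraph assumes that differences in CIT reflect differences in BAT activity, and this is the calculation from which 32 evaluable and 38 enrolled per group are stated. A null CIT result would be judged against a sensitivity that the stated inputs do not support.

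**Working it through.** **Inputs (Section IV.F):** difference 305 kcal/d; SDs 524 and 440; n = 32 per group; two-sample t-test; two-sided alpha 0.05.

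**1. Pooled SD.** √((524² + 440²)/2) = 483.8. The plan's 484 reproduces.

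**2. Power for CIT.** The noncentrality is 305 / (484 × √(2/32)) = 305/121 = 2.52, with 62 degrees of freedom.
- Two-sided (critical t about 2.00): **69.9%** by the noncentral t. The normal approximation gives Φ(2.52 − 1.96) = 71.2%.
- One-sided (critical t about 1.67): **80.2%**. The normal approximation gives 80.9%.

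The stated 80% therefore matches a one-sided test, while the text says two-sided. Other readings do not recover it: 38 per group gives 77.4%, SD 440 alone gives 77.9%, and SD 524 alone gives 63.0%.

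**3. What two-sided 80% would need.** At 32 per group the detectable standardised effect is 0.711.
- Detectable difference: 0.711 × 484 = **344 kcal/d**.
- Sample size for 305 kcal/d: **41 evaluable per group**, or 41/0.85 = 48.2, so 49 enrolled.

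**4. The other statements, same method, 32 per group, two-sided.**

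| Endpoint | Difference / SD | Stated | Recomputed |
|---|---|---|---|
| Oxidative metabolism, thermoneutral (primary) | 0.32/0.45 | 80.0% | 80.0% |
| Oxidative metabolism, cold (primary) | 0.50/0.66 | 84.7% | 84.7% |
| BAT activity volume (secondary) | 39/55 | 80.0% | 79.7% |
| CIT (secondary) | 305/484 | 80% | 69.9% |

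Only the CIT line fails. The dropout step is correct: 32/0.85 = 37.6, so 38.

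**5. Scale of the anchors.** Section III (Estrogen and fat gain) gives premenopausal REE as 1405 (mid-luteal) and 1376 (early follicular) kcal/d. Section IV.D expects the suit to raise REE by about 75%.
- Read as totals: 2530/1405 = 1.80 and 2225/1376 = 1.62. The expected total is 1.75 × 1376 = 2408 to 1.75 × 1405 = 2459 kcal/d, between the two anchors.
- Read as increments: the totals would be 2530 + 1405 = 3935 and 2225 + 1376 = 3601 kcal/d, or 2.80 and 2.62 times REE. Both anchors would also exceed the rise in men reported in Section IV.D for the same cold stimulus, about 4170 − 2300 = 1870 kcal/d.

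**6. What follows for CIT if the anchors are totals.** Subtracting the REE values leaves 1125 and 849 kcal/d, a difference of 276. The difference moves little; the SD is the open question. The documents give no SD for the increment in women under the suit, so the following only illustrates the range. It takes an REE SD of about 159 (standard errors 42 and 43, n = 14: 42√14 = 157, 43√14 = 161) and an assumed correlation r between REE and cold expenditure. The SD of the increment is then √(484² + 159² − 2r × 484 × 159).

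| Assumed r | SD of increment | Power for 305 | Power for 276 |
|---|---|---|---|
| 0 | 509 | 65% | 57% |
| 0.5 | 427 | 80% | 72% |
| 0.8 | 369 | 90% | 84% |

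The men's suit data (± read as SEM, n = 12, r from 0 to 0.8) give SDs of 1019 to 701 and power for 305 of 22% to 40%.

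**The case against.** **CIT is secondary, and the primary endpoint is separately powered.** This stands. A reader might infer from the CIT error that 64 evaluable women are too few. The documents do not support that: both primary statements reproduce at 32 per group, so the sample size has its own support there, on the plan's assumed SDs.

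**The anchors may be what the plan says they are.** A reader might take step 5 as proof that 2530 and 2225 are total cold expenditure. It is the likeliest reading but remains an inference. The plan labels them CIT, the source study is not available here, and the comparison borrows REE from other women and a 75% rise that Section IV.D supports with data from men. A different cold stimulus or a unit error in the source cannot be excluded. This limits the second point to a request for clarification; it does not touch the 70%.

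**The target might look implausible beside the pilot.** Section III reports for five women that "CIT was also attenuated" after ovarian suppression, from 350 to 302 kcal/d, and a reader might conclude that 305 is nearly the whole effect, or might use the pilot SDs to set the detectable difference. Neither is sound. The pilot used a cooling vest for two hours, whereas the trial uses a full suit for 210 minutes. If the anchors are totals, the implied increments are 849 to 1125 kcal/d, of which 305 is 36% to 27%.

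**A one-sided test may have been meant.** The number fits, but the text states a two-sided test and the other three statements reproduce on that basis.

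**Conclusion.** The stated power for CIT is wrong. On the plan's own inputs it is about 70%, ten percentage points below the claim. This rests on no assumption beyond the test that the plan names.

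The mismatch between the anchors and the protocol's definition of CIT is also real, but what the anchors measure is not established. If they are totals, the SD of 484 belongs to a different variable. Power for CIT could then be higher or lower than 70%, depending on an SD that the documents do not give. A reader should not conclude that CIT is badly underpowered, or comfortably powered, from the figures available.

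The planned number of participants is not undermined. The error is confined to a secondary outcome and to the stated rationale for N.

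**What to change.** 1. If 305 and 484 are kept, restate the CIT sentence as about 70% power for 305 kcal/d, or as 80% power for 344 kcal/d, at 32 evaluable per group with a two-sided test.
2. Have the sponsor state, from its own source data, whether 2530 and 2225 kcal/d are total expenditure in the cold or increments over baseline. They should not be relabelled on inference alone.
3. If they are totals, replace them with the difference and SD of the increment and recompute. At 32 per group the difference detectable with 80% power is 0.711 × that SD.
4. Rest the sample size explicitly on the primary endpoint's two power statements, and present CIT as the sensitivity available at that N.

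The cost is one paragraph of protocol text, one look at existing data and a re-run of a short calculation. Enrolment stays at 38 per group. Only if the sponsor wants two-sided 80% power for 305 kcal/d with SD 484 would the numbers rise, to 41 evaluable and 49 enrolled per group.

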The contribution of BAT to EE in humans: Our collaborators, Drs. [name] and [name], have shown that BAT oxidative metabolism contributes to the increased EE during acute cold exposure in humans. In one study, healthy young men (N=12, 23-42 yrs, BMI=24-31 kg·m⁻²) were studied during 3 hr. of mild cold exposure (18°C). Significant uptake of ¹⁸FDG was noted in areas identified as BAT as well as in deep muscles of the thoracic region. Conversely, BAT oxidative metabolism (quantified based on the fast monoexponential decay of ¹¹C-acetate in BAT, k_{mono}) increased significantly (two-fold) in BAT during cold-exposure, but not in adjacent skeletal muscles or subcutaneous adipose tissue (Figure 2).⁶ This indicates a cold-induced activation of oxidative metabolism in BAT, but not skeletal muscle or subcutaneous adipose tissue. **Interestingly, an increased ¹¹C clearance rate was also observed in BAT during measurements obtained at room temperature, suggesting that BAT oxidative metabolism was active even under ambient conditions (Figure 3).** There was an inverse association between BAT activity volume and shivering, suggesting those with

greater BAT volumes produced more heat via non-shivering thermogenesis (NST). In another study, 25 men (22-64 yrs, BMI=23-35 kg·m⁻²) were studied using a similar protocol.⁵ Even in older, overweight men with type 2 diabetes (T2DM) who demonstrate a lower ¹⁸FDG uptake in BAT relative to young, healthy men, BAT oxidative metabolism was increased during cold exposure to similar levels as their young, healthy counterparts.

[figure not shown]

Fig 2. A) BAT oxidative index; B) BAT volume of activity; and C) fractional and D) net glucose uptake in cervicothoracic tissues during acute cold exposure (18 °C). * vs. room Temperature (P<0.01); # vs. BAT (P<0.05). [name] et al., J Physiol, 2015

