Analysis strategy - Statistical analyses will be performed using SAS 9.4. Analyses will begin with descriptive plots of individual variables to evaluate distributional characteristics and for quality assurance. The effect of menopausal status on each endpoint will be estimated using a linear regression model. The endpoint will be the response variable and a variable indicating menopausal status will be the explanatory variable (equivalent to a 2-sample t-test). If a variable that is related to the response variable is not balanced between menopausal groups, that variable will be included in the regression model to eliminate the potential of the effect of menopausal status being confounded by that variable. For all multivariable analyses, regression diagnostics will be used to ensure that the group of explanatory variables are not collinear. Secondary analyses will be performed to investigate whether REE is associated with either BAT

oxidative metabolism or BAT activity volume. Exploratory analyses will investigate the changes in BAT oxidative metabolism and BAT volume of activity associated with GnRH_{AG} treatment (Aim 3) Because these aims are exploratory, results will be reported using descriptive statistics, mean change, and 95% confidence intervals (CIs) for the changes in the primary and secondary endpoints.

G. Summarize Knowledge to be Gained:

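### Loss is met only by over-enrolment, and the separate cold-day regression omits women with a Visit 1 scan but no cold scan, so the SA2 estimate is unprotected if that loss is selective

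*Combined protocol and SAP*

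**What the plan says.** The sample size paragraph of the Data Analysis Plan (IV.F) plans for "32 evaluable participants per group (64 total") and inflates for loss: "Assuming a dropout rate of 15%, 38 participants per group will need to be enrolled to yield the desired sample size of 64 participants". It gives no cause for the 15% and does not separate loss before Visit 2 from a cold session that ends early. Power for the primary endpoint is stated for each condition: "Using a pooled SD of 0.45, we estimate that we will have 80.0% power to detect a difference between groups of 0.32 during thermoneutral conditions", and "Using a pooled SD of 0.66, we will have 84.7% power to detect a difference between groups of 0.50 during cold exposure".

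Under Analysis strategy (IV.F), "The effect of menopausal status on each endpoint will be estimated using a linear regression model", with menopausal status as the explanatory variable and covariates added only for imbalance. The section names no method for missing values, no sensitivity analysis and no comparison of women with and without Visit 2 data.

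The visit descriptions (IV.D) put the thermoneutral scan first and the cold scan ideally within one to two weeks. On the cold day the suit is perfused for 210 min. 11C-acetate is injected at about minute 120 and scanned for 30 min, and 18FDG follows from about minute 150. "Participants will be monitored continuously for shivering using sEMG", but nothing says how a session that ends early will be recorded or analysed.

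**The concern.** The over-enrolment calculation treats the women who are lost as exchangeable with those who remain. That is safe for the head count. It is safe for the SA2 contrast only if missing the cold scan is unrelated to BAT activity, or related to it equally in both groups.

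The cold visit gives some reason to doubt this. A woman whose session ends before the acetate scan is acquired (about minutes 120 to 150) has no cold primary endpoint. One whose session ends after that scan but before the 18FDG imaging keeps the primary endpoint and loses BAT volume. Section III reports, in men, that "There was an inverse association between BAT activity volume and shivering", so a link between BAT and tolerance of the cold is possible.

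Cold-stimulated 11C clearance is one of the two conditions of the primary outcome. As written, the plan discards relevant data already in hand: the woman's thermoneutral clearance, measured shortly before with regions of interest set by that visit's own CT. It also leaves no record from which selective loss could later be judged, whether SA2 turns out positive or null.

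**Working it through.** **1. The plan's own figures.** 32/0.85 = 37.6, so 38 per group; 38 × 0.85 = 32.3 expected to remain. With 32 per group, "using a 2-sided t-test and a type I error rate at 0.05", the noncentral t gives 84.7% power for 0.50/0.66 and 80.0% for 0.32/0.45. All reproduce.

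**2. Inputs for the illustration.** From IV.F: differences 0.32 and 0.50; SDs 0.45 and 0.66; thermoneutral and cold means 0.35 and 0.74 from the study of 12 men. Assumed here: those means apply to the postmenopausal group, so premenopausal means are 0.67 and 1.24; values are normal; within-woman correlation r is 0.4 to 0.8; women below a common Visit 1 cut-off c have no cold scan.

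**3. Loss of the lowest Visit 1 values.** Choose c so that ½[Φ((c − 0.67)/0.45) + Φ((c − 0.35)/0.45)] equals the overall loss. With a the standardised cut-off in a group, the retained women's Visit 1 mean rises by λ(a) = φ(a)/(1 − Φ(a)) SDs, and their cold mean by r × 0.66 × λ(a). The complete-case difference is therefore 0.50 − r × 0.66 × (λ_post − λ_pre).

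| Loss with this cause | Loss pre / post | λ_pre / λ_post | r = 0.4 | r = 0.6 | r = 0.8 |
|---|---|---|---|---|---|
| 15% | 7.2% / 22.8% | 0.149 / 0.391 | 0.436 | 0.404 | 0.372 |
| 7.5% | 3.0% / 12.0% | 0.070 / 0.228 | 0.458 | 0.437 | 0.417 |

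For example, at r = 0.8 in the first row: 0.50 − 0.8 × 0.66 × 0.242 = 0.372. A joint model of both visits returns 0.50 in every cell, because loss depends only on an observed value and the relation is linear.

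In the first row about 35.2 and 29.4 of 38 women remain. Selection also narrows the pooled SD, to 0.64, 0.62 and 0.59 for r = 0.4, 0.6 and 0.8. Power is then 76%, 73% and 71%.

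**4. Direction.** Suppose instead that each group loses a fraction p, related to the cold value with correlation ρ within the group. Its cold mean rises by ρ × 0.66 × φ(z_p)/(1 − p). The last factor is 0.424 at p = 0.25 and 0.109 at p = 0.05, so the net shift is ρ × 0.66 × 0.315, which is 0.062 at ρ = 0.3 and 0.104 at ρ = 0.5.
- Loss 5% pre, 25% post: 0.44 and 0.40.
- Loss 25% pre, 5% post: 0.56 and 0.60.
- Equal loss with equal ρ: 0.50.

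**5. Loss that depends on the unseen cold value.** With a common cut-off on the cold value and 15% loss, complete cases give 0.33. The joint model gives 0.35, 0.38 and 0.42 at r = 0.4, 0.6 and 0.8, so recovery is only partial.

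**6. Random loss.** If all 15% have a Visit 1 scan, the joint model reduces the variance of the cold mean by a factor 1 − 0.15r², a gain of 2.4% to 9.6%.

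**7. Robustness to normality.** In step 3, with 15% loss, c is 0.014, and 94% (pre) and 96% (post) of the women removed have a negative modelled clearance. Repeating it by simulation (1,000,000 per group) with gamma values of the same means and SDs, joined by a Gaussian copula with correlation 0.4 to 0.8, gives complete-case differences of 0.40 to 0.31. The linear joint model gives about 0.46 to 0.45. Attenuation remains, and the correction is incomplete.

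**The case against.** A reader might infer that the women lost will probably be low-BAT shiverers, mostly postmenopausal, so that the planned analysis shrinks the SA2 difference. The documents do not support that reading.
- IV.F gives no cause for the 15%.
- The shivering association in section III is with BAT volume, a secondary endpoint, in men. The same section reports that older men with type 2 diabetes reached similar cold-stimulated oxidative metabolism despite lower 18FDG uptake.
- IV.D expects little shivering from this stimulus (1.6% of maximal voluntary contraction in the earlier study).
- The acetate scan is complete at about minute 150, so stopping later does not lose the primary endpoint.
- Potential Scientific Problems (IV.E) expects more body fat in postmenopausal women under an identical stimulus. If that made the cold easier to bear, premenopausal women could be lost more often and the difference would be inflated.

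It is also fair to say that one regression per endpoint is conventional for two groups of this size, that the normal model in step 3 is crude, and that the joint model helps only partly if loss follows the cold value itself. It does nothing for women lost before Visit 1.

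All of this stands. It limits what can be said about direction and size. It does not supply a missing-data method, use the Visit 1 value, or create a record of why cold scans are missing.

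**Conclusion.** The gap is real and its effect is conditional. The plan protects the number of women but not the SA2 contrast, and it omits women whose thermoneutral clearance is known. Bias arises only if missing the cold scan is related to BAT activity and the loss or its selectivity differs between groups; it may go either way.

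Under the assumed loss of the lowest Visit 1 values, 0.50 is estimated as about 0.37 to 0.44 if the full 15% has this cause and 0.42 to 0.46 if half does. These figures rest on an assumed mechanism, correlation and distribution that the documents do not give, and should not be read as a forecast. In the scenarios examined the joint model was never further from 0.50 than complete cases, and it gave a small precision gain when loss was random. The change is worth making before analysis, but the point does not show that the planned SA2 result will be attenuated.

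**What to change.** 1. For 11C clearance, fit one repeated-measures model to every woman with at least one usable scan: menopausal status, condition, their interaction, and unstructured covariance within woman. Take the SA1 and SA2 contrasts from it. With complete data the unadjusted contrasts equal those of the separate regressions, and covariates can be added for imbalance as already planned. This corrects loss that depends on Visit 1 values when the relation is roughly linear, and corrects only part of any loss that depends on the unseen cold value. It does not extend to 18FDG volume, which is measured only on the cold day.
2. Record the minute and reason for any cold exposure that ends early, and for any missed or unusable cold scan. Report these by group, with the Visit 1 values of women with and without a cold scan.
3. Add a sensitivity analysis that shifts missing cold values down and up, separately in each group. Assigning only low values would favour H2a if more postmenopausal women are missing.

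The cost is a revision of the analysis text, a case-report field, a slightly more complex model and one extra analysis.
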